### **10.3. Patient Withdrawal Criteria**

Patients may withdraw their consent to participate in the study at any time. If a patient withdraws consent, the date and reason for consent withdrawal should be documented. Patients will be encouraged to remain in the CRU to complete all necessary assessments and until the Investigator deems that it is safe to be discharged. Patient data will be included in the analysis up to the date of the withdrawal of consent.

Apart from withdrawal of consent, reasons for early termination of individual patients can include:

- Protocol deviations or patient non-compliance (must be specified on the appropriate eCRF)
- Serious or severe AEs
- Administrative decision by the Investigator or the Sponsor
- Death
- Other (must be specified).

Wherever possible, the tests and evaluations, including those listed for the final visit, should be performed for all patients who discontinue prior to the completion of the study.

## 10.4. Diet, Activity, and Other Restrictions

### 10.4.1. Medication

Patients are required to have completed their treatment for breast cancer (including but not limited to neoadjuvant, radiotherapy, chemotherapy, and immunotherapy) at least 3 months before Screening, with the exception of adjuvant treatment with hormonal or anti-HER2 therapy (which must be stable for at least 3 months prior to Screening, with no planned changes during the study). If a patient is using a standard of care compression sleeve, compression pump, and/or manual lymphatic drainage for at least 4 weeks prior to Screening, they must be agreeable to continuing the same care throughout treatment and through 2 weeks post-study drug discontinuation. If a patient is not using a standard compression sleeve, compression pump, and/or was using manual lymphatic drainage for at least 4 weeks prior to Screening, they must be agreeable to not using these routine lymphatic therapy(s) throughout treatment and through 2 weeks post-study drug discontinuation.

Immunosuppressants or other immune-modifying drugs are not permitted, except for corticosteroids at the discretion of the Investigator. Chronic administration (defined as more than 14 consecutive days) of immunosuppressants or other immune-modifying drugs must be discontinued at least 30 days prior to study drug administration.

Use of any over-the-counter medication (OTC), herbal supplements, or diet aids should be discontinued at least 48 hours prior to dosing, unless approved by the PI and MM. These may be resumed on study, however the following OTC/supplements are not allowed on study:

- Preparations containing a mixture of more than one of the following: kola nut, grape seed extract, or green tea extract
- Goldenseal
- St. John's wort
- Curcumin

Treatment with immunosuppressive or antifibrotic drugs, anti-tumor necrosis factor, immunotherapy, or investigational drugs is not permitted during the study, and must be discontinued at least 30 days prior to Screening.

The following drugs are not permitted during the study, and they must be discontinued at least 28 days or 10 half-lives (whichever is the longer) prior to study drug dosing:

- Fluvoxamine, enoxacin, ciprofloxacin
- Other inhibitors of CYP1A2 (including but not limited to methoxsalen or mexiletine)
- Inducers of CYP1A2 (such as phenytoin), CYP2C9 or 2C19 (including but not limited to carbamazepine or rifampin)
- Any drug associated with *substantial risk for prolongation of the QTc interval* (including but not limited to moxifloxacin, quinidine, procainamide, amiodarone, sotalol)

Use of investigational drugs or devices is not permitted and must be discontinued at least 28 days or 10 half-lives (whichever is the longer) prior to start of dosing.

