**Table 2. Dosing Regimens for Days 1 Through 3 and Thereafter**

Day 1 to Day 3	Day 4 Through Week 26
 LYT-100 500 mg BID  or matching Placebo × 3 days	 LYT-100 750 mg BID  or matching Placebo × 179 days

Abbreviations: BID = twice a day.

Patients will be administered LYT-100 study medication, or placebo, orally with food with approximately 10 to 12 hours between the two daily doses.

Doses may be adjusted according to safety and tolerability to avoid toxicity by adjusting to lower doses in response to patient safety and tolerability issues. If dosing titration is not well tolerated, adjustments to dosing may be made as follows: reductions to 250 mg BID × 2 days (may be longer if needed), 500 mg BID × 2 days (may be longer if needed), 750 mg BID thereafter versus matching placebo.

Patients with breast cancer-related lymphedema will be assessed for safety, tolerability, clinical endpoints, PK, and biomarkers while receiving LYT-100 or placebo over a 26-week (i.e., 6-month) dosing period. If a patient is using a standard of care compression sleeve, compression pump therapy, and/or manual lymphatic drainage within 4 weeks prior to Screening, they must be agreeable to continuing the same routine care throughout the 6-month study treatment period and throughout 2 weeks post-study drug discontinuation. If a patient is not using a standard compression sleeve, compression pump therapy, and/or manual lymphatic drainage ≥ 4 weeks prior to Screening and are not planning to be using these prior to the study, they must be agreeable to not using the lymphedema therapy(s) throughout treatment and 2 weeks post-study drug discontinuation. Patients will be stratified at enrolment into the standard compression sleeve, compression pump therapy, and/or manual lymphatic drainage stratum versus non-compression/non-lymphatic drainage stratum. In addition, patients will be stratified by higher risk of lymphedema progression (axillary lymph node dissection) versus lower risk of lymphedema progression (sentinel node biopsy).

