#### 9.1.1. Treatment Period

This is a double-blind, parallel, placebo-controlled study being conducted to evaluate the safety and efficacy of LYT-100 compared to placebo. This study will be conducted across multiple centers in the US and Australia, with approximately 50 patients randomized to receive LYT-100 or placebo at a ratio of 1:1. LYT-100 dosing is to be titrated starting at 500 mg BID during the first 3 days of dosing, followed by 750 mg BID thereafter.

Patients will take double-blind study medication orally with food BID (approximately 10 to 12 hours between the two daily doses) on an outpatient basis for 26 weeks.

Patients with breast cancer-related lymphedema (BCRL) will be assessed for safety, tolerability, clinical endpoints, PK, and biomarkers while receiving LYT-100 or placebo over the 6-month (26-week) dosing period. If a patient is using a standard of care compression sleeve, compression pump therapy, and/or manual lymphatic drainage at least 4 weeks prior to Screening, they must be agreeable to continuing the same routine care throughout the 6-month (26-week) study treatment period and throughout 2 weeks post-study drug discontinuation. If a patient is not using a standard compression sleeve, compression pump therapy, and/or manual lymphatic drainage  $\geq$  4 weeks prior to Screening and are not planning to be using these prior to the study, they must be agreeable to not using the lymphedema therapy(s) throughout treatment and 2 weeks post-study drug discontinuation.

Following confirmation of study eligibility, patients will be seen in the clinic for their final baseline assessments (Day -1). Patients will begin their BID dosing of study medication on the following morning (Study Day 1) and will continue for 26 weeks, with clinic visits at Weeks 1, 4, 8, 12, 16, 20, and 26.

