All patients will be monitored for safety (including assessment of hematology, serum chemistry, coagulation, and urinalysis parameters, ECGs, vital signs, and AEs). Efficacy assessments will include clinical and QoL measures at time points as delineated in the Schedule of Events (Table 5). Sparse PK samples will be obtained for population PK analysis to determine the variability of LYT-100 drug concentration data in individual patients across multiple clinical sites. Fibrotic and inflammatory biomarkers will be assessed for changes from baseline. With patients using compression sleeves, compression pumps and/or lymphatic drainage as a treatment modality at least 4 weeks prior to and at Screening, they will remain on compression treatments and/or manual lymphatic drainage during the treatment period as noted. Compression sleeves will be removed upon arrival at each study visit and until after the bioimpedance assessment is collected, which should be scheduled at the end of the visit. Time of sleeve

removal will be noted at each study visit. In addition to routine practices such as diet, exercise, or skin care, use or non-use of compression sleeves, compression pumps and/or lymphatic drainage will be recorded in the Patient Diary 1 week prior to each study visit with lymphedema assessments, including frequency of use and the number of hours used on each occasion. Any disruptions in taking study medication as instructed will also be recorded in the Patient Diary.

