## **9.3. Treatment Assignment**

Novotech will prepare a randomization list and will manage the randomization of eligible patients accordingly. A randomization list will be prepared using a statistical software package by a Novotech Biostatistician.

Each patient will be provided with a unique screening number post documentation of informed consent. Once deemed eligible for enrolment in the study, the patient will be assigned a sequential randomization number prior to first dosing. Patients who withdraw from the study during Screening, for any reason, without completing all necessary screening assessments will be considered screen failures. Screen failures will not receive a randomization number; however, source documents may be transcribed onto the electronic Case Report Forms (eCRFs).

Randomization will be stratified by higher risk of lymphedema progression (axillary lymph node dissection) versus lower risk of lymphedema progression (sentinel node biopsy) ([Table 8](#)). Patients will be stratified upon enrolment into the standard compression sleeve, compression pump therapy, and/or manual lymphatic drainage stratum compression versus non-compression/non-lymphatic drainage groups stratum.

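### Section 10.4.1 gives a patient on manual lymphatic drainage two opposite instructions: continue it, and agree not to use it

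*Combined protocol and SAP*

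**What the plan says.** Section 10.4.1 (Medication) has two consecutive sentences on background lymphedema therapy.

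- **Sentence 1, users.** For a patient who has used a compression sleeve, a compression pump and/or manual lymphatic drainage for at least 4 weeks before Screening, the rule is: "they must be agreeable to continuing the same care throughout treatment and through 2 weeks post-study drug discontinuation".
- **Sentence 2, evidently meant for non-users.** It opens with a patient who is not using a sleeve or pump. It then adds, after an and/or, one who "was using manual lymphatic drainage for at least 4 weeks prior to Screening, they must be agreeable to not using these routine lymphatic therapy(s". The restriction runs through treatment and the 2 weeks after it.

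Other parts of the protocol state the rule for users without this conflict:

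- Synopsis, Treatment Period: "they must be agreeable to continuing the same routine care throughout the 6-month study treatment period and throughout 2 weeks post-study drug discontinuation".
- Section 9.1.1: "they must be agreeable to continuing the same routine care throughout the 6-month (26-week) study treatment period", and later in the same section, "they will remain on compression treatments and/or manual lymphatic drainage during the treatment period".
- Section 10.1, Inclusion 14: patients must be willing to maintain their routine, whether that is using or not using these therapies.

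The same status is a randomization factor. Section 9.3 says: "Patients will be stratified upon enrolment into the standard compression sleeve, compression pump therapy, and/or manual lymphatic drainage stratum", as against a stratum without compression or drainage (Table 8).

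**The concern.** Section 10.4.1 is where a site looks up what a patient may and may not do during the study. Read literally, its second sentence tells some drainage users to stop a therapy that the preceding sentence tells them to keep.

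Drainage treats the swelling that the efficacy measures record: limb water content, limb volume and tissue dielectric constant. A patient who stopped would still be counted in the Yes stratum of Table 8 while no longer receiving the therapy that put them there. Any resulting change in the arm would not be due to study drug. The study reads efficacy from the magnitude of effects, and Section 21 says that standardized differences may be used to size later studies, so avoidable variability in these measures is unwelcome.

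**Working it through.** The protocol states no figure on this point. The check is a reading of the two sentences against each type of patient, followed by a count of the exposure.

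**Step 1. Who is caught by each sentence.** Status is taken over at least 4 weeks before Screening. Sentence 2 has two limbs: (i) not using a sleeve or pump; (ii) was using drainage. They are joined by and/or, so both readings are shown.

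| Patient's therapy | Sentence 1 | Sentence 2, read as *and* | Sentence 2, read as *or* |
|---|---|---|---|
| Drainage only | Continue | Limbs (i) and (ii) true: do not use | Do not use |
| Drainage plus sleeve or pump | Continue | Limb (i) false: not caught | Limb (ii) true: do not use |
| Sleeve and pump, no drainage | Continue | Not caught | Not caught |
| None of the three | Not covered | Limb (ii) false: not caught | Limb (i) true: do not use |

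The drainage-only patient gets opposite instructions under either reading. Under *or*, every drainage user does. Under *and*, the patient for whom the sentence must have been written, who uses none of the three, falls outside it. Neither reading gives a workable rule.

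**Step 2. Which sentence is wrong.** The synopsis, both statements in Section 9.1.1 and Inclusion 14 agree with sentence 1. The parallel non-user sentence in the synopsis and Section 9.1.1 begins "If a patient is not using a standard compression sleeve, compression pump therapy, and/or manual lymphatic drainage": there, *not using* governs all three therapies and the words *was using* do not appear. Sentence 2 of Section 10.4.1 is the outlier.

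**Step 3. Exposure if a site followed sentence 2.**

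- Treatment period: 26 weeks × 7 = 182 days, matching Table 7.
- Post-baseline lymphedema visits in Table 5: Weeks 1, 4, 8, 12, 16, 20 and 26 = 7 visits.
- The restriction runs a further 14 days (182 + 14 = 196), but Table 5 schedules no limb measurement after Week 26. Only the 182 days bear on the edema endpoints.

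**Step 4. Direction of the effect.** Treatment is randomized within strata and double-blind (Sections 9.3 and 11.4). A site's reading of this sentence should therefore not depend on the arm, and stopping could occur in either.

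**Step 5. Two smaller mismatches in Section 10.4.1.**

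- Chronic immunosuppressants or other immune-modifying drugs must stop at least 30 days before dosing; Exclusion 2 bars such use within 3 months.
- Stable ongoing anti-HER2 therapy is exempted from the requirement that cancer treatment be complete. Inclusion 4 requires intravenous biologics, with two anti-HER2 agents as its examples, to have been completed at least 3 months before Screening. Inclusion 6 exempts only anti-hormonal regimens from completed adjuvant therapy.

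Section 9.1 enrolls only patients who meet every inclusion and no exclusion criterion, so the stricter criteria already decide both.

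**The case against.** The strongest reply is that the rule is settled elsewhere. A site that stopped a patient's drainage would contradict the preceding sentence, Section 9.1.1 and Inclusion 14. Inclusion 8 also ties therapy status to at least 4 weeks before Screening and throughout the study. A change would be visible, since "use or non-use of compression sleeves, compression pumps and/or lymphatic drainage will be recorded in the Patient Diary" for the week before each visit with lymphedema assessments. All of this stands. It fixes the intent and limits the harm, but it does not correct Section 10.4.1, and the protocol gives no order of precedence between that section and Section 9.1.1.

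A second reply is that *was using* could describe a former user who must not restart. This is strained: sentence 2 uses the same window of at least 4 weeks before Screening that sentence 1 uses for current users, and nothing in it says that the therapy had ended.

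A reader might also infer that the synopsis and Section 9.1.1 share the fault, because a drainage-only patient is not using a sleeve. The documents do not support that. Following a sentence that tells users to continue, and qualified by the patient not planning to use these therapies, the wording naturally describes non-users.

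**Conclusion.** Wrong as written, minor. Section 10.4.1 contradicts itself for drainage users, and the second sentence is the one in error.

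The number of patients affected is not given and may be zero. For any patient affected, the exposure is up to 26 weeks off drainage, across 7 post-baseline lymphedema visits. This assumes that a site follows sentence 2 literally from the start of treatment and that the patient stays to Week 26.

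Three stronger readings should be resisted:

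- **Bias in the treatment comparison.** The sentence applies equally in both blinded arms. What it could add is noise.
- **A size of harm from one patient's weight.** With about 25 patients per arm, one patient is 1/25 = 4% of an arm mean, but that holds for any patient and any deviation. It says nothing about how far the measures would move.
- **A wider eligible population through the 30-day washout or the anti-HER2 exemption.** A 30-day minimum does not override the 3 months in Exclusion 2, and Inclusions 4 and 6 still apply. These are consistency notes only.

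**What to change.** Replace the second sentence on lymphedema therapy in Section 10.4.1 with wording to this effect:

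> A patient who is using none of the three therapies (compression sleeve, compression pump, manual lymphatic drainage), and has used none for at least 4 weeks before Screening, must agree to use none of them during treatment and for 2 weeks after stopping study drug.

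This covers only the last row of the table in the working and leaves every user under sentence 1. Saying *not using any of* in the matching sentences of the synopsis and Section 9.1.1 is optional.

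Two minor consistency edits in Section 10.4.1 can go in at the same time. Change the 30-day washout for chronic immunosuppressants or other immune-modifying drugs to 3 months, keeping the corticosteroid allowance. Delete the anti-HER2 exemption so that the section matches Inclusions 4 and 6. Loosening the inclusion criteria instead would widen eligibility and is not proposed here.

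The cost is wording only, handled through the amendment process in Section 27.1. No procedure, visit, patient or analysis changes.

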#### **10.4.2. Smoking**

All patients are required to abstain from tobacco or nicotine-containing products in the 30 days prior to dosing and for the duration of the study until completion of the final follow-up visit.

#### **10.4.3. Contraception**

No estrogen preparations (e.g., oestradiol, ethinylloestradiol) are to be used throughout the trial for contraception, hormone replacement therapy, or menopausal replacement therapy.

Acceptable, highly effective double contraception is defined as a condom AND one other form of the following:

- Established hormonal contraception (oral contraceptive pills [OCPs], long-acting implantable hormones, injectable hormones) except for preparations containing oestradiol, ethinylloestradiol
- A vaginal ring or an intrauterine device (IUD)
- Documented evidence of surgical sterilization at least 6 months prior to Screening (e.g., tubal occlusion, hysterectomy, bilateral salpingectomy, or bilateral oophorectomy for women or vasectomy for men [with appropriate post-vasectomy documentation of the absence of sperm in semen] provided the male partner is a sole partner).

Women not of childbearing potential must be postmenopausal for  $\geq 12$  months. Postmenopausal status will be confirmed through testing of FSH levels  $\geq 40$  IU/mL at Screening for amenorrhoeic female patients. Females who are abstinent from heterosexual intercourse will also be eligible.

Periodic abstinence (e.g., calendar, ovulation, symptothermal, post-ovulation methods) and withdrawal are not considered highly effective methods of birth control. Patient complete abstinence for the duration of the study and for 1 month after the last study treatment is acceptable.

Female patients who are in same sex relationships are not required to use contraception.

Males must be surgically sterile ( $> 30$  days since vasectomy with no viable sperm), abstinent, or if engaged in sexual relations with a WOCBP, the patient and his partner must be surgically sterile (e.g., tubal occlusion, hysterectomy, bilateral salpingectomy, bilateral oophorectomy) or using an acceptable, highly effective contraceptive method from Screening until study completion, including the follow-up period. Acceptable methods of contraception include the use of condoms and the use of an effective contraceptive for the female partner that includes: OCPs, long-acting implantable hormones, injectable -hormones, a vaginal ring, or an IUD. Patients with same sex partners (abstinence from penile-vaginal intercourse) are eligible when this is their preferred and usual lifestyle.

#### **10.4.4. Food**

Patients are required to take study medication with food.

#### **10.4.5. Other Restrictions**

All patients must be willing to abstain from direct whole body sun exposure from 2 days prior to dosing and until final study procedures have been conducted. Patients should be instructed to avoid or minimize exposure to sunlight (including sunlamps), use an SPF 50 sun block, or higher, wear clothing that protects against sun exposure, and avoid concomitant medications known to cause photosensitivity.

All patients must refrain from blood or blood product donation > 250 mL within 28 days of Screening, and blood or blood products donation is not permitted from Screening until the final visit.

## **11. TREATMENT OF PATIENTS**

### **11.1. Description of Study Drug**

The LYT-100 drug product and matching placebo are presented as follows:

- LYT-100, 250 mg and matching placebo – Size 0 or 1, Swedish orange opaque, hard-gelatin capsules.

The capsules are packaged in high-density polyethylene (HDPE) bottles and a white, polypropylene screw cap with an induction sealed aluminum inner seal. The IPs should be stored at a controlled room temperature of 15°C to 25°C.

### **11.2. Prior and Concomitant Medications**

#### **11.2.1. Prior Medications**

All medications, including over-the-counter (OTC) medications, vitamins, and herbal supplements, taken during the 30 days prior to the first study drug administration will be recorded and reviewed by the Investigator to determine whether the patient is suitable for inclusion in the study.

#### **11.2.2. Concomitant Medications**

All medications, including OTC medications, vitamins, and herbal supplements, taken by patients during the course of the study will be recorded in the eCRF and coded using the most current World Health Organization (WHO) drug dictionary available at Novotech. Prior and concomitant medications will be listed by patient and summarized by anatomical therapeutic chemical (ATC) and Preferred Term (PT).

